We propose a 2-year study to examine how infant egg consumption (age of introduction and frequency of intake) influences physical growth, obesity, cardio-metabolic health, risk of food allergy, and cognition development in mid-childhood and adolescence. We will use existing data from two US longitudinal birth cohorts that tracked mother-child dyads from pregnancy to adolescence: 1) Project Viva (1999-present) that enrolled 2,341 pregnancies and followed children at delivery, 6 months (m), then yearly from 1 year (y) to 15 y of child age, and 2) the Infant Feeding Practices Study II (IFPS II, 2005-2007) that enrolled 3,033 pregnancies with surveys in late pregnancy, neonatal (1 m), then monthly from 2 m to 12 m of infant age, and at 6 y. For **Aim 1**, we will classify infants based on their age of egg introduction: never, <2 m, 2-3 m, 4-5 m, 6-8 m, 9-11 m, and ≥ 12 m. We will compare physical growth, obesity, cardio-metabolic health, food allergy, and cognition test scores in mid-childhood and adolescence. We will fit multivariable linear or logistic regression models with fractional polynomial functions of infant age of egg introduction. Both linear (e.g., earlier introduction, higher probability of the outcome) and non-linear (e.g., threshold effect) associations will be tested. For **Aim 2**, we will classify infants based on their frequency of egg intake: never, <once/week, once/week, 2-4 times/week, nearly daily or daily, and ≥ 2 times/day. We will use similar analytic methods mentioned above to compare their later outcomes. Finally, we will create an average probability of multiple child outcomes to balance across different aspects of child health and development. We will identify the lowest-risk infant egg consumption when the corresponding average predicted probability of the related adverse outcomes is the lowest.

Section 2: Detailed Research Plan

1) Background Information:

Early-life nutrition is highly influential in establishing lifelong health. During the first 1,000 days of life from conception to the end of the second year, nutrient exposure through both maternal and infant diet can significantly impact organ development and regulate gene expression through epigenetic events including DNA methylation and histone modification¹. While early exposure to processed, energy dense foods can 'malprogram' developmental pathways toward disease risk, early-life consumption of whole foods (e.g. hen eggs) with superior nutrition can protect against chronic disease throughout the life course.

As an affordable, highly digestible, low-calorie matrix of complete protein, essential fatty acids (e.g. docosahexaenoic acid [DHA]) and micronutrients (e.g. choline, vitamins A and B12, and carotenoids), hen eggs contribute >50% of adequate intakes of critical nutrients during infancy^{2,3}. Given their high nutritional value, it seems logical to include eggs as a dietary staple to promote optimal child development. However, past guidelines from health care professionals and federal agencies to limit exposure of infants to common allergenic foods such as peanuts and eggs have traditionally led to slow introduction or complete egg avoidance for infants in the first six months to one year of life^{4,5}.

With recent work highlighting that peanut introduction in early infancy can protect against peanut allergy development in childhood^{6,7}, there has been a shift in recommendations for complementary feeding practices. Contrary to traditional recommendations (ESPAI, 1999⁸ and AAP, 2000⁵), recent national (AAP, 2019)⁹ and international (EAACI, 2014)¹⁰ guidelines report that there is no evidence to suggest that withholding the introduction of allergenic foods to infants after 4-6 months is protective against allergy development. However, compared with peanuts, the ideal age for egg introduction into the infant diet is still debated (AAP, 2019)⁹. Egg allergy is often perceived as one of the most common food allergies in early childhood by health professionals and parents, contributing to a major consumer perception obstacle for the egg industry and a potential barrier to widespread egg infant consumption^{10,11}. In support of current recommendations, more recent work has reported either no influence¹² or even a protective effect¹³ of egg introduction at 4-6 months of age on allergy risk in infants older than 12 months. A recent systematic review and meta-analysis of 146 interventional and observational studies of timing of allergenic food introduction concluded that there was moderate-certainty evidence to support early egg introduction at 4-6 months to reduce egg allergy (risk ratio [RR], 0.56; 95% CI, 0.36-0.87; p=0.009)¹⁴. Five of the 6 studies reported a protective effect of early egg introduction on egg allergy (RR point estimate, 0.22-0.69). In the outlier study, Bellach et al. reported that infants randomized to egg white powder had a doubled risk of egg sensitization at 1 year of age versus those in the control rice powder group (5.6% versus 2.6%; RR 2.20; 95% CI, 0.68-7.14), however these results did not reach statistical significance (p=0.24)¹⁵.

An optimal infant egg introduction strategy must consider multiple childhood and food-influencing factors, including both age of egg introduction, frequency (amount) of egg consumption, and egg fraction¹⁴. Tran et al.¹⁶ recently investigated how early (0-6 months), usual (7-12 months), and delayed (avoidance during first year) timing of egg introduction influenced food sensitization. They reported that introduction of eggs at 0-6 months versus 7-12 months was associated with no increased risk of egg allergy at 1 year of age; further, total

avoidance of eggs in the first year of life increased the risk of egg sensitization. This data suggests the potential existence of an age threshold at which delayed egg introduction will increase egg allergy risk. This age threshold may be between 7-12 months (a relatively wide range for infants); however, additional research is required to narrow down to a more precise age. Other work suggests that not only the exposure window, but also the amount of egg consumed is an important consideration in infant egg introduction strategies. In 4-5-month-old infants, Natsume¹⁷ reported that a small amount of heated egg powder (50 mg per day from 6-9 months of age and 250 mg per day thereafter until 12 months) was effective in preventing egg allergy in high-risk infants receiving optimal eczema treatment. We are unaware of any work that has specifically examined how the frequency of infant egg consumption affects allergy response or other health indices in infants. Treatment options for egg and other food allergies are limited¹⁸. Prevention strategies may be informed with a more precise understanding of the age and frequency of infant egg consumption that protects against allergic responses.

Importantly, complementary food exposure practices should balance allergy concerns with the nutritional benefits of eggs and other health interests of children¹⁹. Although allergic outcomes associated with any complementary infant feeding practice is critical, a full assessment of infant egg introduction approaches should include an evaluation of multiple childhood health outcomes, not just allergy alone, as untimely food introduction strategies can strongly influence whole-body health and development^{4,20}. A recent meta-analysis from Eaton et al.²¹ concluded that there was little quality evidence to assess the impact of animal source proteins (versus fortified grains or no intervention) on childhood growth and development. With eggs specifically, traditional guidelines that focused overwhelmingly on allergy have resulted in a scientific record that is inadequate to assess how early egg consumption influences a broader spectrum of childhood health indices including physical growth, obesity, cardio-metabolic health, and cognition. However, limited work does suggest that early egg introduction can positively influence diet quality, as recently demonstrated by Papanikolaou et al.²² who reported that consumption of eggs in 6-9 month-old infants was associated with higher nutrient intakes including protein, choline, lutein + zeaxanthin, DHA, phosphorus, and VitB12. Supporting the work of others²³, their data also demonstrated that infant egg consumers had lower total and added sugar intake, highlighting eggs as a potentially important early-life disease risk reduction strategy as infant sugar consumption has been associated with childhood obesity²⁴. However, as far as we are aware, no studies have directly tested the effects of early egg exposure on childhood obesity. These associations between early egg exposure and nutrient intake are further supported by clinical data linking infant egg consumption with improvements in childhood growth and development. In a 6-month randomized controlled study in 6-9 months old infants, Lanotti et al. (2017)²³ reported that consumption of 1 egg per day (versus no egg) increased length and weight-for-age z score and reduced the prevalence of stunting (by 47%) and underweight (by 74%). These improved growth responses could be attributed to enhanced infant blood levels of choline, betaine, methionine, as well as DHA²⁵.

According to the lipid hypothesis, high blood cholesterol is a causative agent and primary prevention target of cardiovascular disease (CVD)²⁶. A consequence of this hypothesis was the recommendation to limit intake of high cholesterol foods, including eggs. Eggs are a

rich source of dietary cholesterol (~200 mg) and have been estimated to contribute about a quarter of the daily cholesterol intake in U.S. adults and children^{27,28}. However, recent research suggests that the low-density lipoprotein cholesterol (LDL-C) raising effects of dietary eggs in adult populations is largely negligible and highly variable depending on individual genetic and metabolic factors²⁹. Further, increased cholesterol intake from eggs has been associated with an improved lipoprotein profile and high-density lipoprotein (HDL) functionality in adults²⁷. Our understanding of how infant egg consumption influences surrogate lipid markers of CVD risk (LDL-C, HDL-C, and triglycerides) in childhood is insufficient. However, a previous study reported that egg consumption in children aged 8-12 years old had no effect on serum lipid concentrations and even resulted in a less atherogenic lipoprotein distribution pattern in a subset of children with small LDL particles³⁰. Considering that metabolic disease risk factors in early life can be predictive of future disease risk patterns in adulthood³¹, more research is required to understand how infant exposure to eggs, a significant source of dietary cholesterol and other important bioactive nutrients, impacts childhood health.

DHA (22:5n-3), an essential long-chain fatty acid found in conventional and omega-3 enriched eggs, is critical for early fetal growth and the development of neurological function³². Pregnant and nursing women are advised to consume at least 200 mg of DHA daily; however, dietary intake is below recommendations in the majority of US women during pregnancy³³. Previous work has reported that children from mothers supplemented with DHA from delivery until 4 months have better sustained attention at 5 months of age³² and improved psychomotor development measured at 2.5 years of age³⁴. Further, maternal supplementation of choline, another egg-rich nutrient has been associated with protection against cognitive impairment due to prenatal alcohol exposure³⁵. However, although a recent prospective cohort study reported that egg consumption was associated with enhanced cognitive performance in adults³⁶, the impact of infant egg consumption on cognitive performance during childhood is not known.

Summary of Current Knowledge and Research Priorities:

- Allergy concerns have traditionally led to slow introduction practices or complete avoidance of eggs during the first year of life, despite the high nutrient value of eggs.
- Although recent research supports early infant egg exposure to reduce childhood egg allergy, optimal egg introduction strategies (age, frequency/amount, fraction) are still debated among parents and healthcare professions, creating a barrier for widespread infant egg consumption.
- Optimal infant egg consumption guidelines must balance allergy concerns with broader assessments of child health and development, including physical growth, obesity, cardio-metabolic health, and cognitive development.
- Currently, there is insufficient knowledge of how the age of infant egg introduction and frequency of egg intake influence whole-body child health and development.

2) Research Project Objectives and Hypotheses:

[figure not shown]
Objectives: To examine the longitudinal associations of infant age of egg introduction (**Aim 1**) and frequency of infant egg intake (**Aim 2**) with physical growth, obesity, cardio-metabolic health, risk of food allergy, and cognition development in mid-childhood and adolescence.

Hypotheses: The effects of infant age of egg introduction and frequency of egg intake will vary by the child outcome of interest (**Hypothesis 1**). We predict a non-linear association between age of egg introduction and the average probability of multiple child outcomes (i.e., stunting, underweight, obesity, high risk of metabolic syndrome, food allergy, and cognitive delay), with the optimal age being a time point that falls between 6-12 months (**Hypothesis 2**). We also predict a non-linear association between frequency of infant egg intake and the average probability of multiple child outcomes, with the optimal frequency being 2-4 times per week (**Hypothesis 3**).

3) Project Design:

Sample/Data. We propose a 2-year study to examine the extent to which two important aspects of infant egg consumption (i.e., age of introduction and frequency of intake) influence physical growth, obesity, cardio-metabolic health, risk of food allergy, and cognition development in mid-childhood and adolescence. Guided by a life course framework (**Figure 1**), we will use existing secondary data from two US longitudinal birth cohorts that tracked mother-child dyads from pregnancy to adolescence: 1) **Project Viva** (1999-present, N=2,128 newborns) that followed children at delivery, 6 months (m), 1 year (y), 2 y, 3 y, 4 y, 5 y, 6 y, 7 y, 8 y, 9 y, 10 y, 11 y, 12-13 y, 14 y, and 15 y of child age,³⁷ and 2) **Infant Feeding Practices Study II** (IFPS II, 2005-2012, N=3,033 newborns) that followed children at neonatal (1 m), 2 m, 3 m, 4 m, 5 m, 6 m, 7 m, 9 m, 10 m, 12 m, and 6 y of child age.^{38,39} The PI has access to both datasets, and has 3 publications on infant nutrition, early childhood diet, growth, and obesity using Project Viva^{40,41} and IFPS II⁴² data since 2014. These two studies have a similar study design and complementary measures of child outcomes, which provide a unique opportunity for comprehensive analysis on the health effects of infant egg consumption and also external replication of findings.

Exposure measures (infant egg consumption). We will focus on age of introduction and frequency of intake as the key exposure measures of infant egg consumption, because evidence

Infant Egg Consumption | Child Health and Cognition | Clinical Guidelines

Figure 1. Conceptual framework on effects of infant egg consumption

supports their potential influences on child health and development⁴³. We recognize that other aspects of infant egg consumption such as different egg fractions (i.e., white vs yolk⁴⁴) may also influence child outcomes but they were not collected in Project Viva or IFPS II.

Age of egg introduction. At **Project Viva** visits, the age of infant egg introduction was asked at 6-m and 12-m using the same question - “How old was your baby when you first fed him/her eggs”. In the **IFPS II**, mothers reported their infant’s intake of 18 types of foods in the past 7 days through monthly surveys from 2-12 m of infant ages. The question used for infant food intake was - “In the past 7 days, how often was your baby fed each food listed below? Include feedings by everyone who feeds the baby and include snacks and night-time feedings.” “Eggs” were one of the 18 types of foods. Accordingly, we will derive the infant age of egg introduction from IFPS II mothers’ monthly responses to infant egg consumption. Our previous analysis on infant dietary patterns showed that 1.7% and 63.0% of IFPS II infants had been introduced eggs by 6 m and 12 m of age, respectively⁴².

Frequency of egg intake. At the 2-y survey in **Project Viva**, the frequency of infant egg intake in the past month was obtained from the mothers’ response to the question - “Please check the box that best represents how often your child eats each of the foods listed, on average, in the past month”. One of the food items for this question was “Whole eggs”. Response options for the frequency of consuming “Whole eggs” included “never”, “<once/week”, “once/week”, “2–4 times/week”, “nearly daily or daily”, and “≥2 times/day”.

The same question was asked again at surveys at 3 y and 7 y. As mentioned above, mothers in the IFPS II reported their infant's intake of eggs in the past 7 days through the monthly surveys from 2-12 m of infant ages. Infant egg intake was reported as the number of feedings per day or per week. Our analysis on infant dietary patterns showed the mean egg intake among IFPS II infants was 0.01 (SD, 0.10) and 0.27 (SD, 0.37) serving/week at 6 m and 12 m, respectively⁴².

Child outcome measures. We will focus on child physical growth, obesity, cardio-metabolic health, risk of food allergy, and cognition development (**Figure 1**). These child outcomes were chosen because they 1) may be influenced by infant egg consumption (see '**Background**'), 2) are clinically important, and 3) were measured in Project Viva and/or IFPS II.

Physical growth. In Project Viva, birth weight was obtained from birth certificates. Research staff measured children's length/height, weight, and waist circumference at 6 m (infancy), 3 y (early childhood), 7 y (mid-childhood), 12-13 y (early teen), and 14-15 (mid-teen)^{37,45}. Additional data on child weight and length/height were obtained from medical records at well-child visits. In IFPS II, mothers reported infant birth weight and length in neonatal survey; weight, length, and age at their most recent doctor's visit in 3-m, 5-m, and 7-m, 12-m, and 6-y surveys^{38,42}. Body mass index (BMI) was calculated as, weight in kg/(height in meters)². We will define stunting as height-for-age z score < -2, and underweight as sex- and age-specific BMI < 5th percentile according to World Health Organization (WHO) Growth Standards^{46,47}.

Obesity. In both Project Viva and IFPS II, we will define child obesity as sex- and age-specific BMI \geq 95th percentile according to WHO Growth Standards^{46,47}. In Project Viva, skinfold thickness was measured at 3 y, 7 y, 12-13 y, and 14-15 y. In addition, fat, lean and trunk fat mass were measured through whole-body dual X-ray absorptiometry (DXA) scans performed at 7 y, 12-13 y, and 14-15 y. Accordingly, we will calculate fat mass index (FMI, kg/m²), lean mass index (LMI, kg/m²), and trunk fat mass index (TFMI, kg/m²).

Cardio-metabolic health. At the 7-y and 12-13-y visits in Project Viva, the child's systolic (SBP) and diastolic blood pressure (DBP) were measured with automated oscillometric monitors. In addition, the child's fasting blood was used to measure plasma glucose, insulin, adiponectin, and C-reactive protein (CRP), serum total cholesterol (TC), triglycerides (TG), and HDL⁴⁸. We will calculate LDL as, total cholesterol – HDL – (triglycerides/5). We will estimate insulin resistance through the homeostatic model assessment of insulin resistance (HOMA-IR = [glucose mg/dL \times insulin μ IU/mL]/405). A metabolic syndrome z score was derived by calculating the mean of five age- and sex-specific internal z scores for waist circumference, SBP, inverted HDL, natural log-transformed TG, and natural log-transformed HOMA-IR⁴⁸.

Risk of food allergy. In Project Viva, mothers reported the child's food allergy annually from 2 y to 11 y, at 12-13-y and 14-15-y of child age through the questions, - "In the past month, has your child avoided any foods because of a food allergy, intolerance, or sensitivity?", and "If yes, please specify". More details on food allergy were reported at the 7-y and 12-13-y visits using the question, - "Has your child ever had an allergic reaction to fish, shellfish, sesame seeds, peanuts or tree nuts?". In addition, at the 7-y and 12-13-y visits, food allergen sensitization of the child was defined as any serum specific IgE level of 0.35 IU/mL or greater to one of the food allergens listed, i.e., egg white, milk, wheat, peanut, and soybean⁴⁹. In the IFPS II, mothers reported whether their infant had food allergy in the past 2 weeks at 2-12 m of infant ages. Additional information on infant food allergy was collected at 4, 9, and 12 m:

whether food allergy (e.g., allergic reaction, sensitivity, or intolerance) happened at the first time of eating, exposure pathway, initial age, allergic symptoms, doctor visit, methods for testing food allergy, diagnosis, treatments, and food allergens including eggs. At the 6-y follow-up, mothers reported the child's status and history of food allergy, initial age, symptoms, testing methods, diagnosis, treatments, outgrowing food allergy, and food avoidance.

Cognition development. In Project Viva, the child's cognition development, including intelligence, visual-motor, and memory-learning, was measured at 3 y and 7 y of age⁵⁰. For the intelligence domain, trained research staff administered the Peabody Picture Vocabulary Test-3rd edition (PPVT-III, a test of receptive language) at 3 y of age, and the Kaufman Brief Intelligence Test-2nd edition (KBIT-II, verbal and non-verbal intelligence) at 7 y of age. For the visual-motor domain, research staff administered the Wide Range Assessment of Visual Motor Abilities (WRAVMA) at the 3-y visit. WRAVMA includes the fine motor (pegboard), visual spatial (matching), and visual motor (drawing) subtests. Subtest scores were combined to yield the total WRAVMA score. At the 7-y visit, staff administered the WRAVMA visual motor (drawing) subtest only. For the memory-learning domain, staff administered the design memory and picture memory subsets of Wide Range Assessment of Memory and Learning (WRAML) at the 7-y visit. These two subset scores were combined to yield the total WRAML score.

Effect modifier. We are interested in effect modification by child sex (Boys vs Girls).

Confounders. Potential confounders include family income; health history of family members; parental education attainment, employment, and preconception BMI; and maternal intelligence, age, race/ethnicity, marital status, parity, pregnancy complications, prenatal vitamins, smoking, and delivery method; early mode of infant feeding including breastfeeding duration and exclusivity. We will also adjust for child actual age at assessments.

Data analysis. All our analyses will be first conducted among boys and girls separately to examine the potential sex differences (if significant, sex-stratified results will be reported).

For **Aim 1 (infant age of egg introduction)**, we will first classify the infants based on their age of egg introduction: never, <2 m, 2-3 m, 4-5 m, 6-8 m, 9-11 m, and 12 m. Then we will compare their physical growth, obesity, cardio-metabolic risk profile, risk of food allergy, and cognition test scores in mid-childhood and adolescence using Chi-square tests (categorical outcomes) or ANOVA tests (continuous outcomes). We will fit multivariable linear (continuous outcomes) or logistic (binary outcomes) regression models with fractional polynomial functions of infant age of egg introduction, adjusted for significant confounders. Both linear (e.g., earlier introduction, high probability of the outcome) and non-linear (e.g., threshold effect) associations will be tested. The non-linear trend will be examined through visualization of scatter plots and statistical tests of polynomial term of infant age of egg introduction in the regression models. If the polynomial terms of age are not significant, we will drop it and consider the association to be linear.

Then, we will fit a mixed effect model (SAS PROC MIXED) for continuous outcomes (height z-score and BMI z-score) and a generalized linear mixed effect model (SAS PROC GLIMMIX) for binary outcomes (obesity and diagnosis of food allergy) that were measured repeatedly across multiple age points. The mixed effect model will include random intercepts, random slopes for age effects, and autoregressive variance-covariance matrix across different time points. Independent variables in the model will include infant age of egg introduction, outcome age point (mid-childhood and adolescence), the 2-way interaction term (infant age of

egg introduction × outcome age point), and significant covariates. The 2-way interaction term quantifies the extent to which infant age of egg introduction can affect the specific outcome. The PI has experience with using mixed effect models for examine child growth measures and multiple publications in this area.^{51,52}

For **Aim 2 (frequency of infant egg intake)**, we will first classify the infants based on their frequency of egg intake: never, <once/week, once/week, 2–4 times/week, nearly daily or daily, and ≥ 2 times/day. Then, we will use similar analytic methods mentioned above for Aim 1 to compare their health and developmental outcomes.

In addition, we will create an **average probability of multiple child outcomes** to balance across different aspects of child health and development using the methods published by Oken et al.⁵³ for identifying the lowest-risk exposure level when multiple outcomes are considered. Specifically, we will focus on 6 binary child outcomes including stunting, underweight, obesity, high risk of metabolic syndrome (e.g., z score $\geq 95^{\text{th}}$ percentile), food allergy, and cognitive delay (e.g., standardized cognition score < 85 points). We will use estimates from aforementioned logistic models to generate predicted probabilities of each of the 6 adverse outcomes when the independent variable of infant egg consumption (i.e., age of egg introduction or frequency of egg intake) varies across the observed range within our study sample. We will calculate the average probability of the 6 outcomes, assuming these outcomes are equally important. We will identify the lowest-risk infant egg consumption when the corresponding average probability of the 6 adverse outcomes is the lowest.

We will handle missing data with Multiple Imputation.⁵⁴ Specifically, we will first generate 20 replicates of datasets (PROC MI in SAS) with imputed values for missing data on infant egg consumption, child outcomes, and significant covariates, based on a bayesian approach. The 2nd stage is to use standard statistical methods (e.g., Linear Regression) to fit the model of interest to examine the association between infant egg consumption and the specific outcome within each of the 20 imputed datasets. The 3rd stage is to pool the analytic results from all 20 imputed datasets to get the average estimates of the association (PROC MIANALYZE). The PI has experience with Multiple Imputation for large datasets.⁵⁵

All our analyses will be first conducted among boys and girls separately to examine the potential sex differences. A formal interaction test will be conducted by including the interaction term of egg consumption and sex into the regression models. If the interaction term is significant, sex-stratified results will be reported. Otherwise, sex-pooled analytic results will be reported.

Statistical Power. We expect sufficient statistical power for our hypothesis-driven data analyses for both Aims, because 1) the 2 cohorts had relatively large sample sizes (N=2,128 for Project Viva and N=3,033 for IFPS II), which are sufficient to detect a small odds ratio (1.46 for Project Viva, 1.38 for IFPS II with type 1 error being 0.05 and power being 0.8) of binary child outcomes (e.g., food allergy) between infants with different egg consumption (e.g., egg introduced at ≥ 12 m vs 6-8 m) or a small effect (effect size=0.054 for Project Viva, 0.051 for IFPS II) of infant egg consumption on continuous outcomes (e.g., intelligence score); 2) most child outcomes were measured repeatedly; 3) infant egg consumption varied largely within cohorts.

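### IFPS II dates egg introduction only from past-7-day reports, so an infant who reacted to a first egg and stopped can be classed as not introduced, which tilts the allergy comparison toward early introduction

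*Combined protocol and SAP*

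**What the plan says.** The exposure is defined in Section 2, 3) Project Design, under Age of egg introduction. Project Viva mothers were asked at 6 and 12 m: "How old was your baby when you first fed him/her eggs". IFPS II mothers were instead asked about recent intake: "In the past 7 days, how often was your baby fed each food listed below". From those answers the plan states that "we will derive the infant age of egg introduction from IFPS II" mothers' responses; it names no other source.

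The surveys are described in that section as running "through monthly surveys from 2-12 m of infant ages". The schedule under Sample/Data reads "5 m, 6 m, 7 m, 9 m, 10 m, 12 m, and 6 y of child age" and so lists no survey at 8 or 11 m. The plan reports that "1.7% and 63.0% of IFPS II infants had been introduced eggs by 6 m and 12 m of age".

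Under Risk of food allergy, extra IFPS II items at 4, 9 and 12 m record whether the allergy "happened at the first time of eating, exposure pathway, initial age, allergic symptoms", and which foods were responsible, eggs included. These appear only as outcome data.

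The Aim 1 groups are "never, <2 m, 2-3 m, 4-5 m, 6-8 m, 9-11 m, and 12 m" (the last is written ≥12 m in the opening summary). No rule says where an IFPS II infant with no egg reported through 12 m belongs, and nothing addresses infants who tried egg and stopped.

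**The concern.** A past-week question detects current eating, not first eating. For infants who keep eating egg this mostly delays the recorded age, since a later survey picks them up. For an infant who reacted and was not given egg again, no later survey can.

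That error is tied to the outcome: the reaction causes both the missing exposure record and the allergy record. Allergic infants leave their true introduction-age group and join the not-introduced group. Risk rises in the second and falls in the first, so earlier introduction looks protective even if it does nothing.

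The affected contrast is the one the plan uses as its power example (food allergy, ≥12 m against 6-8 m). Food allergy is also one of the six outcomes averaged to choose the lowest-risk age. The planned safeguards do not reach the problem. The listed confounders include no history of infant reactions, and multiple imputation does not act on a wrongly recorded absence of egg, because that is not a missing value.

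**Working it through.** **The plan's own figure.** Statistical Power gives a detectable odds ratio (OR) of 1.38 for IFPS II (N = 3,033, α = 0.05, power 0.8), with no baseline risk or group split, so it cannot be reproduced from stated inputs. It fits an assumed 10% baseline and equal groups: 10% against 0.138/1.038 = 13.3%, two-sided, gives power 0.808. It serves here only as a yardstick.

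**Step 1: chance of missing one feeding.** For a single feeding on a random day, P(missed) = 1 − 7/(days between surveys).
- Monthly gap: 1 − 7/30.4 = 77%.
- Two-month gap (7 to 9 m, 10 to 12 m): 1 − 7/60.9 = 88.5%.
- All nine listed infant surveys: 9 × 7 = 63 of about 304 days from 2 to 12 m, so about 79% missed.
- 6 to 12 m, when nearly all introduction is recorded (1.7% rising to 63.0%): surveys at 7, 9, 10 and 12 m cover 28 of about 183 days, so about 85% missed.
- If feeding lasted 7 days before stopping, 13 start days per gap lead to detection: 1 − 13/30.4 = 57% to 1 − 13/60.9 = 79% missed.

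**Step 2: infants misfiled.** Assumption: 1-3% of 3,033 react to a first egg and stop, i.e. 30-91 infants. At 79% missed, 24-72 are misfiled. Taking the plan's 63.0% as the 7-day-rule count, the groups are 0.37 × 3,033 ≈ 1,122 not introduced and 0.63 × 3,033 ≈ 1,911 introduced.

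**Step 3: effect on allergy at 6 y.** Further assumptions: 10% background risk and half of reactors still allergic, so a misfiled infant's risk is 0.5 + 0.5 × 0.10 = 0.55. Suppose age of introduction has no effect and both true groups have 10% risk.

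| | 24 misfiled | 72 misfiled |
|---|---|---|
| Not introduced | (0.10 × 1,098 + 0.55 × 24)/1,122 = 11.0% | (0.10 × 1,050 + 0.55 × 72)/1,122 = 12.9% |
| Introduced | (0.10 × 1,935 − 0.55 × 24)/1,911 = 9.4% | (0.10 × 1,983 − 0.55 × 72)/1,911 = 8.3% |
| OR against a fixed 10% | 1.11 | 1.33 |
| OR, not introduced against introduced | 1.18 | 1.63 |

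**Step 4: sensitivity to the assumptions.**
- With 85% missed (26-77 infants), the last row becomes 1.20-1.69.
- With 5% background (misfiled risk 0.525), the risks are 6.0% against 4.4% (OR 1.39) and 8.0% against 3.2% (OR 2.63).
- With 20% background (misfiled risk 0.60), they are 20.9% against 19.5% (OR 1.09) and 22.6% against 18.5% (OR 1.28).

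**The case against.** **Coding.** A reader might infer that every such infant is filed as never introduced. The documents do not support that. A feeding inside a window is caught, and the plan does not say whether no egg through 12 m means never or ≥12 m. The choice matters: the regressions use a polynomial in introduction age, and never has no age. If coded ≥12 m, these infants sit at the late end of that curve; if coded never, they may enter only the unadjusted group comparison. This stands, and the point is worded accordingly.

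**What the allergy items show.** A reader might also infer that they record the first egg feeding. They record a reaction, its age, pathway and allergen. That dates first feeding only if egg was eaten directly and the reaction came at first eating; otherwise it gives an upper bound. Whether initial age links to egg when several foods are named cannot be seen from the documents.

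**Outcome-dependent correction.** Redating only reactors makes exposure depend on the outcome. This is the strongest objection, and it rules the corrected variable out as the sole definition. About 1.7% of 3,033 = 52 infants were introduced by 6 m. Adding 10 reactors there gives (5.2 + 5.5)/62 = 17%, OR about 1.9 against 10%. But the 1-3% assumption implies only (30 to 91) × 1.7/63.0 × 0.79 = 0.6-1.9 misfiled reactors in that cell. One or two give (5.2 + 0.55)/53 = 10.8% or (5.2 + 1.1)/54 = 11.7%, OR 1.10-1.19.

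**Size.** If 10% is the risk before reactors are added, and the 6-19 captured reactors stay in the introduced group, that group's risk is 0.10 + 0.45 × (6 to 19)/1,911 = 10.1-10.4%. The observed OR is then 1.09-1.27, below 1.38. However, in that scenario correct classification gives the introduced group 0.10 + 0.45 × 30/1,935 = 10.7% to 0.10 + 0.45 × 91/1,983 = 12.1%, hence an OR of 0.93-0.81. The distortion is 1.09/0.93 to 1.27/0.81, again about 1.2-1.6.

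**Scope.** The mechanism concerns food allergy in one cohort. Project Viva's direct question is not exposed to it.

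**Conclusion.** The concern holds in bounded form. Followed as written, the IFPS II derivation can, and for a single feeding usually would (about 77-88%), place an infant who reacted and stopped in the not-introduced group because of the allergy itself. The bias favors earlier introduction.

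The direction follows from the text; the size does not. The reaction rate, persistence and background risk are all assumptions, and the counts apply 37% to everyone enrolled, although only those followed to 6 y contribute. Under the main set (1-3%, one half, 10%) the spurious OR is about 1.1-1.3 against a fixed comparator and 1.2-1.6 in full; the latter range spans the plan's detectable 1.38. A lower background risk makes it larger and a higher one smaller. It would go too far to say that any IFPS II allergy finding would be an artifact: the documents do not give the number of reactors.

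The two cohorts also measure different things under one name, first-ever feeding and first captured weekly intake. Agreement between them can support direction but not an age cut-point. The change should be made, though it does not invalidate the design.

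**What to change.** Under Age of egg introduction, add a second IFPS II derivation for the food-allergy outcome and the six-outcome average:

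- Where a 4-, 9- or 12-m allergy item names egg and the pathway is direct feeding, take the infant out of the not-introduced group. Use the initial age as introduction age if the reaction was at first eating, and otherwise as an upper bound.
- Report results under this rule and the 7-day-only rule. Do not conclude from IFPS II that earlier introduction benefits allergy unless the result holds under both.
- Label the remaining group 'no egg in any surveyed week', and state whether it is analyzed as never or as ≥12 m.
- Limit the replication claim against Project Viva to direction rather than age cut-points.

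The cost is a derivation rule, some recoding in a dataset to which the investigator already has access, and one extra set of results. The downside is that the correction exists only for reactors, relies on recalled ages and needs the item to link to egg. It depends on the outcome, so it should sit beside the 7-day rule and not replace it.
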